7.5.3. Pharmacokinetic Parameter Analyses

The following plasma PK parameters, as data permit, will be calculated for total Mo and PUF Mo on Day 1 and Day 15 using noncompartmental methods with Phoenix[®] WinNonlin[®] (Certara USA Inc., Princeton, New Jersey) Version 8.0 or higher, or SAS Version 9.4 or higher (SAS Institute Inc., Cary, North Carolina), as applicable. Calculations will be based on the actual sampling times relative to the actual reference ALXN1840 dosing times recorded during the study.

- Time delay between the time of dosing and time of appearance of Mo concentration (T_{lag}) in plasma (Day 1 and Day 15)
- Maximum observed concentration (C_{max}) (Day 1 and Day 15)
- Time to maximum concentration (T_{max}) (Day 1 and Day 15)
- Trough (predose) concentration observed at the start of the dosing interval (C_{trough})
- Time of last quantifiable concentration (T_{last}) (Day 1 and Day 15)

- Observed concentration at the end of the dosing interval (C_{τ} , where $\tau = 24$ h) (Day 1 and Day 15)
- Area under the plasma concentration versus time curve (AUC) from time 0 to the last quantifiable concentration (AUC_t) (Day 1 and Day 15)
- AUC from time 0 to infinity (AUC_{∞}) (Day 1 only)
- AUC over the dosing interval (AUC_{τ}) (Day 1 and Day 15)
- Apparent terminal-phase elimination rate constant (λ_z) (Day 1 and Day 15)
- Terminal elimination half-life ($t_{1/2}$) (Day 1 and Day 15)
- Apparent total body clearance (CL/F) (Day 1 and Day 15)
- Apparent volume of distribution (V_d/F) (Day 1 and Day 15)
- Accumulation ratio (AR) calculated as C_{\max} , C_{trough} , and AUC after repeat dosing on Day 15 divided by those after initial dosing on Day 1:
 - $C_{\max, \text{Day15}}/C_{\max, \text{Day1}}$
 - $C_{\text{trough}, \text{Day15}}/C_{\text{trough}, \text{Day1}}$
 - $AUC_{\tau, \text{Day15}}/AUC_{\tau, \text{Day1}}$

Additional plasma PK parameters may be calculated if deemed appropriate.

For the PK analysis, below the limit of quantification (BLQ) values prior to the first measurable concentration will be set to zero with the rest of all other BLQ values treated as missing

Pharmacokinetic parameters derived from plasma concentrations of total Mo and PUF Mo will be presented in data listings and summarized by analyte and day using the following descriptive statistics: number of participants, arithmetic mean, SD, arithmetic CV, GM, GMCV, median, minimum, and maximum.

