## 4. STUDY DESIGN

### 4.1. Overall Design

This is a single-arm, open-label, repeat-dose (30 mg/day) study designed to assess the effects of ALXN1840 administration on Cu balance in healthy participants.

This study will be conducted in a minimum of 2 groups. The first group will consist of approximately 6 participants and no more than 8 participants. The second group may only be initiated after the Safety Review Committee (SRC; defined in [Section 9.7](#)) reviews safety information (all AEs, safety laboratory data, and vital signs) through Day 18 and agrees that it is safe to continue enrollment to complete the study. If ceruloplasmin concentrations or AE findings are suggestive of over-depletion of Cu, the SRC may propose a dose reduction to 15 mg/day for remainder of the study population.

This is a single arm study. Following screening and enrollment, participants will have a Run-in Period to support diet equilibration (Day -7 through Day -5) and measure of pretreatment Cu and Mo balance (Day -4 through Day -1). Following the Run-in Period, participants will be administered ALXN1840 at 30 mg/day for 15 days (Day 1 through Day 15). ALXN1840 will be administered orally after an overnight fast, and participants will remain fasted for a minimum of 2 hours following each dose administration. Following completion of the 15 days dosing period, participants will remain the clinical research unit (CRU) for an additional 16 days until discharge on Day 31.

Total intake and output will be measured continuously from Day -4 through Day 30 with Day 1 through Day 15 representing the ALXN1840 treatment period and Day 16 through Day 30 representing the post-treatment period. The collection period will support assessment of Cu balance and Mo mass balance including assessment at steady state and terminal elimination.

Participants will return to the CRU for a final study visit on Day 43 ± 2 days, approximately 28 days after the final dose of ALXN1840, to conclude the safety follow-up period.

Participants meeting all study entry criteria prior to Cu/Mo controlled diet initiation are eligible for enrollment. At the time of enrollment, participants will be assigned a subject number for the study.

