concentration cannot distinguish whether the Mo is complexed with Cu and albumin (as in TPC), free active ALXN1840 drug, intermediate hydrolysis products, or molybdate which may be from ALXN1840 hydrolysis. To better characterize the amount of non-TPC bound ALXN1840 and its degradation products, plasma ultrafiltrate Mo (PUF Mo), which represents the free parent drug (ALXN1840), short-lived intermediate hydrolysis products, and molybdate, will be measured. Total Mo and PUF Mo concentrations also include physiologic molybdate concentrations from dietary micronutrient molybdate intake. While it is not feasible to separate and quantify ALXN1840 directly in the plasma, total Mo PK and PUF Mo PK provide surrogate measures to characterize ALXN1840 exposure. To better characterize the ADME of ALXN1840, the PK of both total Mo and PUF Mo will be characterized and described.

Single dose administration of the enterically-coated ALXN1840 under fasted conditions in healthy participants resulted in a peak total Mo concentration, as stable TPC, at approximately 4.54 hours with a half-life of approximately 51 hours. In Study WTX101-HV-106, a 60-mg dose demonstrated a total Mo time to maximum concentration ( $T_{max}$ ) of approximately 6 hours with up to 14% of the total Mo represented as PUF Mo, which also peaked at approximately 6 hours post dose. By 24 hours, PUF Mo had declined to approximately 3-5% of the total Mo. These findings are consistent with results from the Phase 2 Study WTX101-201 in patients with WD. Given the much longer half-life of total Mo, a repeat dose study of 15 days duration will support steady state assessment of ALXN1840 ADME (as measured by total Mo and PUF Mo). In addition, complete collection of Mo over the ALXN1840 treatment period as well as the 15-day terminal elimination period may support a complete assessment of Mo balance for the study.

As this study represents the first repeat dose study in healthy participants, dosing duration will be limited to 15 days. Safety laboratory tests will be monitored at least every 3 days with individual and cohort stopping criteria in place if significant safety risks are identified. In addition, if findings of Cu depletion or toxicity are identified in the initial study group by Day 18, the dose of ALXN1840 may be reduced to 15 mg/day for the remainder of the enrolled participants.

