7.1.3.2. Baseline Characteristics

The following Baseline characteristics will be summarized:

- LBC ($\mu\text{mol}/\text{L}$)
- LBC categorization based on normal reference range (female: $<0.7 \mu\text{mol}/\text{L}$, 0.7 to $5.9 \mu\text{mol}/\text{L}$, $>5.9 \mu\text{mol}/\text{L}$; male: $<0.9 \mu\text{mol}/\text{L}$, 0.9 to $4.4 \mu\text{mol}/\text{L}$, $>4.4 \mu\text{mol}/\text{L}$)
- NCC ($\mu\text{mol}/\text{L}$)
- NCC categorization based on normal reference range ($<0.8 \mu\text{mol}/\text{L}$, 0.8 to $2.3 \mu\text{mol}/\text{L}$, $>2.3 \mu\text{mol}/\text{L}$)
- Albumin (g/L)
- International Normalized Ratio (INR)
- Total bilirubin ($\mu\text{mol}/\text{L}$)
- Direct bilirubin ($\mu\text{mol}/\text{L}$)
- Alanine aminotransferase (ALT) (IU/L)
- Aspartate aminotransferase (AST) (IU/L)
- Gamma-glutamyltransferase (GGT) (IU/L)
- Platelets ($10^9/\text{L}$)
- Leukocytes ($10^9/\text{L}$)
- Creatine Kinase (IU/L)
- Total Plasma Cu ($\mu\text{mol}/\text{L}$)

- Total plasma Cu; categorization based on normal reference range (low: < 11.33 $\mu\text{mol/L}$ [$< 720 \text{ ng/mL}$]; normal: 11.33 - 26.12 $\mu\text{mol/L}$ [$720 - 1660 \text{ ng/mL}$]; high: > 26.12 $\mu\text{mol/L}$ [$> 1660 \text{ ng/mL}$])
- PUF-Cu ($\mu\text{mol/L}$)
- Total plasma Mo ($\mu\text{mol/L}$)
- PUF-Mo ($\mu\text{mol/L}$)
- Cp (mg/L)
- 24-Hour urinary Cu ($\mu\text{g/day}$)
- 24-Hour urinary Mo ($\mu\text{g/day}$)
- Categorization of baseline lab values (ALT, AST, GGT, platelets, leukocytes, creatine kinase) based on the reference ranges (L: Low, N: Normal, H: High)

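### Read as first quantifiable sample, Tlag in SAP 7.5.3 is 0 for total Mo on Day 15 whatever the true lag, and on Day 1 wherever pre-dose dietary Mo is quantifiable

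*SAP*

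**What the plan says.** SAP 7.5.3 lists noncompartmental parameters for total Mo and PUF Mo, to be calculated where the data allow. The first is Tlag, on Day 1 and Day 15, described as the "Time delay between the time of dosing and time of appearance of Mo concentration" in plasma. No algorithm follows. The nearest rule is a general one for the PK analysis: "below the limit of quantification (BLQ) values prior to the first measurable concentration will be set to zero", with all other BLQ values treated as missing.

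Protocol 4.2 describes what is being measured:
- "Total Mo and PUF Mo concentrations also include physiologic molybdate concentrations from dietary micronutrient molybdate intake".
- After a single fasted dose in healthy participants, total Mo peaked "at approximately 4.54 hours with a half-life of approximately 51 hours".
- The tablet is enteric-coated: "Single dose administration of the enterically-coated ALXN1840 under fasted conditions" is how the section introduces those figures.

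SAP 7.1.3.2 lists "Total plasma Mo" and PUF-Mo among the baseline characteristics to be summarised.

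Nothing corrects Mo for its pre-dose level. SAP 7.5.2 provides absolute and percent change from baseline for the PD analytes and biomarkers. SAP 7.5.1 and 7.5.3 provide neither for Mo, and SAP 9.3, on additional statistical methods, is marked not applicable.

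**The concern.** Time to appearance is a sound definition of lag when the analyte is absent before dosing. Here it is present for two separate reasons: carry-over from earlier doses on Day 15, and dietary molybdate on both days. A rule that looks for the first quantifiable sample finds it at pre-dose and returns 0, so it cannot show the delay that an enteric coating would be expected to produce.

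Two consequences follow. A Day 15 row of zeros could be read as evidence of immediate absorption. SAP 7.5.3 also asks for an arithmetic CV, geometric mean and geometric CV of every parameter; with every value 0 the arithmetic CV is 0/0 and the geometric statistics carry no information. On Day 1, participants just above and just below the LLOQ at pre-dose would share one summary although their Tlag values mean different things.

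**Working it through.** The documents state no Tlag value, so there is no figure to reproduce. The check asks what the definition returns.

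**Inputs.** Half-life of total Mo 51 h and Tmax 4.54 h (Protocol 4.2); one dose every 24 h, 14 doses before the Day 15 dose (Protocol 4.1); samples at pre-dose and 1, 2, 3, 4, 5, 6, 8, 12 and 24 h (Protocol Table 2). The LLOQs and the baseline plasma Mo level are not given and are varied below.

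**1. Day 15, total Mo.** The fraction remaining after one dosing interval is r = 2^(−24/51) = 0.722. The Day 15 pre-dose level, relative to the drug-derived level 24 h after dose 1, is

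(1 − r^14)/(1 − r) = (1 − 0.0104)/(1 − 0.722) ≈ 3.56.

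The ratio is within participant, so it does not depend on dose if the dose is constant. It cannot fall below 1 for any half-life: at 24 h it is 2.00 and at 12 h it is 1.33.

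**2. Profiles on the sampling grid.** A one-compartment superposition used the inputs above, assumed true lags of 0.5, 1.5 and 2.5 h, assumed baselines of 0, 0.5, 2 and 5% of Day 1 Cmax, and assumed LLOQs of 1 and 10% of Day 1 Cmax: 3 × 4 × 2 = 24 scenarios. Appearance was taken as the first quantifiable sample.

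| | Day 1, pre-dose below LLOQ | Day 1, pre-dose at or above LLOQ | Day 15 |
|---|---|---|---|
| True lag 0.5 h | between 0 and 1 h | 0 | 0 |
| True lag 1.5 h | between 1 and 2 h | 0 | 0 |
| True lag 2.5 h | between 2 and 3 h | 0 | 0 |

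The Day 15 pre-dose level was 2.74 to 2.81 times Day 1 Cmax, and Day 15 Tlag was 0 in all 24 scenarios.

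**3. PUF Mo.** For a single 60 mg dose, Protocol 4.2 gives PUF Mo as up to 14% of total Mo, with both peaking at about 6 h, and adds: "By 24 hours, PUF Mo had declined to approximately 3-5% of the total Mo". Total Mo falls by 2^(−18/51) = 0.783 between 6 and 24 h, so PUF Mo at 24 h is 0.03 × 0.783/0.14 = 17% to 0.05 × 0.783/0.14 = 28% of its peak. If that share persists and exposure scales with dose, the Day 15 trough at 30 mg/day is 3.56 × 30/60 = 1.78 times the level measured 24 h after the single 60 mg dose. For a participant on the 15 mg/day that the SRC may choose, it is 3.56 × 15/60 = 0.89 times. Quantifiable troughs are likely, but no LLOQ is given to confirm it.

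**4. Day 1.** The BLQ rule zeroes only values that are BLQ; a quantifiable pre-dose value stands as measured. The share of participants with forced zeros therefore equals the share with quantifiable pre-dose Mo: 0 to 100%.

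**5. Alternative rule.** In the same noise-free profiles, the first sample above that day's pre-dose value came at 1, 2 and 3 h for true lags of 0.5, 1.5 and 2.5 h, on both days. The last sample before that rise is at 0, 1 and 2 h, so the true lag is bracketed on the 1 h grid.

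**The case against.** The strongest reply is that the SAP never equates appearance with the first quantifiable sample and never says that Tlag is 0 when the pre-dose value is quantifiable. The BLQ sentence is general, and the parameters are calculated only where the data allow, so Tlag could go unreported. This stands in part: the zero comes from the natural reading, which the BLQ rule supports, and not from a written algorithm. But nothing in the SAP tells the analyst to withhold Tlag or to correct for the pre-dose level.

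A reader might go further in three ways that the documents do not support:
- That Day 15 Tlag is 0 in every participant for both analytes. The 51 h half-life is for total Mo only; PUF Mo has neither a stated half-life nor an LLOQ.
- That Day 1 Tlag will be 0. Protocol 4.2 establishes that dietary Mo is present, not that it exceeds the LLOQ. Listing it as a baseline characteristic suggests values are expected, but the SAP also provides for BLQ results.
- That Tlast shares the defect. It is the time of the last quantifiable concentration. If that is the last scheduled sample, the value is correct and marks the interval for AUCt.

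On importance the objection is right. Tlag is not in the parameter list of Protocol 9.4.3, is not named in any objective or endpoint, and does not enter AUC, Cmax, half-life or the accumulation ratios. Hourly early samples limit its resolution to about 1 h, and the individual concentration-time plots in SAP 7.5.1 would still show a delay.

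**Conclusion.** The point holds and is minor. For total Mo on Day 15, the definition returns 0 for participants dosed through Day 14 who have a pre-dose sample, whatever the true lag. This rests on reading appearance as first quantifiable and on total Mo being quantifiable 24 h after a dose. The second assumption is safe: the protocol reports PUF Mo at 24 h as a percentage of total Mo, and the Day 15 pre-dose level is about 3.56 times the 24 h level after dose 1. For PUF Mo on Day 15 the same result is likely but unproven. On Day 1 it is conditional on quantifiable pre-dose Mo, and a forced 0 could not be told apart from a truly short lag. The Cu balance endpoint is unaffected.

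**What to change.** In SAP 7.5.3:

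- **Day 15:** delete Tlag for both analytes, or derive it by the Day 1 rule below. Deletion is simpler. A margin proportional to the pre-dose value would be large on Day 15, where that value is about 2.7 to 2.8 times Day 1 Cmax, and could delay detection of the rise.
- **Day 1:** define Tlag as the last sampling time before concentration first exceeds the participant's own pre-dose value by more than a pre-specified margin for assay imprecision. Take the margin from the assay validation, separately for total Mo and PUF Mo, and state it in the SAP before parameters are derived. Where pre-dose is BLQ, the existing rule sets it to zero and the first quantifiable value counts as the rise. Where the pre-dose sample is missing, Tlag is missing.
- **Tlast:** leave unchanged.

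The cost is SAP wording and one figure per analyte from the validation report. No new samples are needed and no other parameter changes.

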### Overall Design

This is a single-arm, open-label, repeat-dose (30 mg/day) study designed to assess the effects of ALXN1840 administration on Cu balance in healthy participants. The safety and tolerability of ALXN1840 in healthy participants will also be assessed. ALXN1840 pharmacokinetics (PK) in plasma as measured via total Mo and plasma ultrafiltrate (PUF) Mo will be determined after single and repeated dosing along with total Mo mass balance at steady state.

**Disclosure Statement:** This is an open-label, 2-period study with 1 arm.

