**Table 2: Schedule of Pharmacokinetic/Pharmacodynamic and Safety Assessments on Day 1 and Day 15**

Time point (h) a	Pre-dose b	0	1	2	3	4	5	6	8	12	24
ALXN1840 (total Mo) and PUF Mo PK	X		X	X	X	X	X	X	X	X	X
Plasma total Cu, ceruloplasmin, ceruloplasmin-bound Cu, and LBC	X		X	X	X	X	X	X	X	X	X
ECG (triplicate)	X					X					

a Time points are relative to dosing (0 hours) on Day 1 and Day 15.

b Pre-dose should be collected within 1 hour prior to dosing.

Note 1: Windows for PK/PD time points will be defined as  $\pm 10\%$  of the nominal time point.

Note 2: The 24-hour PK/PD samples after Day 1 and Day 15 dosing are to be collected at pre-dose on Day 2 and at approximately 0800 am on Day 16.

Note 3: When multiple procedures are scheduled to occur at the same time, the following order of events should be strictly adhered to whenever possible: ECG, vital signs, blood sampling, study intervention administration, and meal.

Abbreviations: Cu = copper; LBC = labile-bound copper; Mo = molybdenum; PK = pharmacokinetic; PUF = plasma ultrafiltrate.

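### For total Mo, SAP 7.5.3 derives Day 1 parameters that rest on extrapolating about three quarters of AUC-infinity, and fits the Day 15 half-life with no dietary-Mo correction and no stated window

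*SAP*

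**What the plan says.** - **Parameters.** SAP 7.5.3: "The following plasma PK parameters, as data permit, will be calculated for total Mo and PUF Mo on Day 1 and Day 15" by noncompartmental methods. The list includes "AUC from time 0 to infinity" for Day 1 only, and lambda_z, "Terminal elimination half-life ($t_{1/2}$) (Day 1 and Day 15"), CL/F and Vd/F for both days. It gives no extrapolation limit, span or fit criterion. SAP 9.3, on additional statistical methods, is marked not applicable.
- **Day 1 sampling.** Protocol Table 2, Note 2: "The 24-hour PK/PD samples after Day 1 and Day 15 dosing are to be collected at pre-dose on Day 2". Dosing is daily, so the first dose cannot be followed alone beyond that sample.
- **Half-life.** Protocol 4.2 reports that total Mo after a single fasted dose peaks "at approximately 4.54 hours with a half-life of approximately 51 hours".
- **Dietary Mo.** Protocol 4.2: "Total Mo and PUF Mo concentrations also include physiologic molybdate concentrations from dietary micronutrient molybdate intake". SAP 7.5.1 and 7.5.3 contain no subtraction for it.
- **Washout sampling.** The notes to Protocol Figure 1 schedule PK samples on Days 16, 18, 21, 24, 27 and 30, about 24 to 360 h after the last dose. SAP 7.5.3 does not say which of them enter the Day 15 terminal fit.
- **Use.** Protocol 3 makes terminal elimination of Mo after steady-state dosing part of a secondary endpoint. The Synopsis (Overall Design) says that plasma PK "will be determined after single and repeated dosing along with total Mo mass balance at steady state".

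**The concern.** There are two separate problems.

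**Day 1.** A profile shorter than half of one half-life cannot support a terminal slope. AUC-infinity would be mostly extrapolation from that slope, and CL/F and Vd/F would inherit the uncertainty. Because the Synopsis promises PK after single dosing, the tabulated values could be read as single-dose PK.

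**Day 15.** A roughly constant dietary level added to a declining drug level flattens the tail on the log scale, so the fitted half-life is too long. The later the window, the larger the effect. With neither a correction nor a window stated, the same data can yield different half-lives for a secondary endpoint, and Day 15 Vd/F moves with them.

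**Working it through.** The documents state no extrapolated share and no plasma background for Mo, so there is no plan figure to reproduce. All results below come from a one-compartment oral model.

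**Inputs (Protocol 4.2).** Half-life 51 h; Tmax 4.54 h, or 6 h after 60 mg in Study WTX101-HV-106. At 24 h after 60 mg, PUF Mo was about 3–5% of total Mo.

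**Day 1**

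1. Share of a half-life observed: 24/51 = 0.47.
2. k = ln 2/51 = 0.01359 per h. Solving Tmax = ln(ka/k)/(ka − k) gives ka = 0.949 (4.54 h) or 0.661 (6 h) per h.
3. Extrapolated share = [ka·exp(−24k) − k·exp(−24ka)]/(ka − k). The second term is negligible.
   - Tmax 4.54 h: 0.6847/0.9352 = 73.2%.
   - Tmax 6 h: 0.4770/0.6474 = 73.7%.
4. The documents do not say whether the 51 h was baseline-corrected. At an assumed 45 h the share is 70–71%; at 40 h it is 67–68%.
5. Noise: with an assumed 10% error per sample, a fit to the 8, 12 and 24 h samples (16/51 = 0.31 half-lives) gives a half-life with a 5th–95th percentile range of about 25–253 h. About 5.5% of fits show no decline.

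**Day 15**

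1. Superpose 15 daily doses. Drug-derived Mo at 24, 72, 144, 216, 288 and 360 h is about 76–78%, 40–41%, 15%, 5.7%, 2.1% and 0.8% of the Day 15 peak. With a background of 1% of peak, the Day 30 sample would read about 1.8%, more than half of it dietary.
2. Upper bound on background: treat all PUF Mo at 24 h as dietary and assume dose proportionality. In units where one 30 mg dose contributes 1, the model concentration 24 h after 60 mg is 2 × 0.732 = 1.464 and the Day 15 peak is 3.415. So 0.03 × 1.464/3.415 = 1.3% and 0.05 × 1.464/3.415 = 2.1% (2.2% with Tmax 6 h). PUF Mo also contains drug and its hydrolysis products, so the true level should be lower.
3. Add a constant background and fit the log-linear slope (true value 51 h):

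| Assumed background, % of Day 15 peak | All six samples, Days 16–30 | 24–144 h only |
|---|---|---|
| 0.2 | 53 h | 51.3 h |
| 1 | 61 h | 52.7 h |
| 2 | 68 h | 54.4 h |
| 2.2 (upper bound) | 70 h | 55 h |

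4. Over 0.2–2%, Day 15 Vd/F is inflated by 5–32% (six samples) or 1–5% (24–144 h). Day 15 CL/F as dose/AUCtau moves only from +0.5% to −1.5%.

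**The case against.** **Day 1 matters little.** The listed PK objective is steady-state PK. Single-dose PK appears only in a design sentence, and the SAP's proviso about data permitting lets unreliable values be dropped. This stands in part: the proviso gives permission but no criterion, so nothing says when a value is withheld. It does argue for listing and flagging the values, not deleting them.

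**The Day 15 size is assumed.** This stands. The direction is secure; the size depends on a background level that the documents do not give and on a window that they do not name. In the same model, choosing among the last three to six samples by adjusted R-squared selects all six at every background tested, giving 53, 61 and 68 h at 0.2%, 1% and 2%. An early window would leave little bias.

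**The data remain visible.** SAP 7.1.3.2 summarizes baseline total Mo and SAP 7.5.1 plots individual profiles. True, but neither step corrects the reported half-life.

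**Readings that go too far.**
- A reader might infer that the half-life will come out near 100 h. In the model that needs the last three samples alone and a background close to the upper bound (99 h at 2%). The SAP proposes no such window.
- A reader might infer that copper and Mo are handled inconsistently, because SAP 7.5.2 takes change from Baseline for the copper markers. The exploratory endpoint for ceruloplasmin, ceruloplasmin-bound Cu and LBC is itself defined as a change, so the contrast shows no inconsistency in PK handling.

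**Conclusion.** Both parts hold for total Mo, and the SAP should be changed. On Day 1, 73–74% of AUC-infinity would be extrapolated if the half-life is 51 h, and still 67–71% at 40–45 h, with no stated limit. On Day 15, the half-life is biased upward by an unknown amount: about 2–17 h over all six samples, and less than 4 h over 24–144 h, for an assumed background of 0.2–2% of peak.

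These sizes rest on one compartment, no absorption lag, dose proportionality, a constant dietary level and, for the upper bound, ultrafilterable dietary molybdate. Confidence is high in the omissions and the direction of the bias, and lower in its size.

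The documents do not support extending the point to Day 15 CL/F or to the primary copper-balance result. Nor does it touch Day 1 Cmax, Tmax or AUCtau. All PK output is descriptive, so no test result is at risk.

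**What to change.** In SAP 7.5.3:

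- **(a) Total Mo, Day 1.** Do not summarize AUC-infinity, lambda_z, t1/2, CL/F or Vd/F. List them only, flagged with the percent extrapolated. Keep every other Day 1 parameter: Cmax, Tmax, Tlag, Tlast, Ctrough, C24, AUCt, AUCtau and the accumulation ratios. Record this in SAP 4.1 as a change from Protocol 9.4.3; SAP 4.1 now reports no changes.
- **(b) Total Mo, Day 15 lambda_z and t1/2.** Subtract each participant's Day 1 pre-dose Mo and make this the main estimate, with uncorrected values as supportive. Fit terminal log-linear samples from Days 16–30, with at least 3 points. Exclude the first sample whose measured value falls below a stated multiple of pre-dose (twice, for example) and all later ones. If pre-dose is BLQ, no subtraction or cut-off is needed, in line with the existing rule that "below the limit of quantification (BLQ) values prior to the first measurable concentration will be set to zero". Set the start of the window by a stated goodness-of-fit rule, not at a fixed 24 h. If 10% of the amplitude at 24 h declined with an assumed 100 h half-life, a fit forced to start at 24 h would return only 58–60 h.
- **(c) Day 15 CL/F and Vd/F.** CL/F = dose/AUCtau and Vd/F = CL/F divided by lambda_z, with AUCtau and lambda_z both baseline-corrected.
- **(d) PUF Mo.** State whether the same correction applies, since Protocol 4.2 says PUF Mo also includes dietary molybdate.

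Subtraction with the twice-pre-dose cut-off was simulated under one compartment, with the fit starting on Day 16 and an assumed 10% error. Median corrected half-lives were 51.0–52.0 h at 0.2–2.2% background. At 2.2% the 5th–95th percentile range was 46.5–57.0 h, against 66–74 h uncorrected over six samples. All profiles kept at least 3 points. The goodness-of-fit start was not tested, and the multiple of two is a reviewer's choice.

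The cost is SAP wording, one SAP 4.1 entry and one supportive table; a few Day 1 parameters are no longer summarized. The samples are already scheduled, and the Mo-controlled diet runs from Day -7 through Day 30, so the pre-dose value reflects the same diet.
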